**Table 2: Alternative Ten Day Dosing Schedule**

Treatment	Cycle 1			Between Cycles	Cycles 2 -4			Month 1 – 6 after end of final cycle
	Day 1-5 and 8-12	Between Day 13-22	Day 23-28	Day 29 - 56	Day 1-5 and 8-12	Between Day 13-22	Day 23-28	
Decitabine	1X daily				1X daily			
DLI		Once per dose algorithm*				Once per dose algorithm*		
Ruxolitinib	2x daily							→
Rescreen for eligibility				Continuous rescreening per section 8.5				

\* See [section 8.2, Table 4](#): DLI dose escalation algorithm

**Table 3: Five Day schedule for Cycles 3 and 4 if CR is achieved after Cycle 2**

Treatment	Cycle 3		Between Cycles	Cycle 4		Month 1 – 6 after end of final cycle
	Day 1-5	Between Day 6 - 16	Day 17 - 56	Day 1-5	Between Day 6-16	
Decitabine	1X daily			1X daily		
DLI		Once per dose algorithm*			Once per dose algorithm*	
Ruxolitinib	2x daily					→
Rescreen for eligibility			Continuous rescreening per section 8.5			

\* See [section 8.2, Table 4](#): DLI dose escalation algorithm

## 8.1 Chemotherapy Regimen

The administration of the preparative regimen will follow institutional drug and supportive care guidelines. Dose and/or schedule adjustments consistent with the standard of care may be made on an individual patient basis as needed for safety.

**Ruxolitinib** 5 mg twice daily orally beginning Day 1 and through Cycle 1. Consider dose increase to 10 mg twice daily in cycles 2 through 4 if platelets recover to over  $>100 \times 10^9/L$ . Ruxolitinib will continue through six months after the completion of the final cycle. See [section 8.4](#) for toxicity dose modification.

**Decitabine:** 20 mg/m^2 IV daily, on the following possible schedules: day 1-10 for cycles 1-2 (alternative: day 1-5 and day 8-12 with no weekend infusion); day 1-5 for cycles 3-4 (if CR achieved after Cycle 2). There are no dose modifications.

## 8.2 DLI

Within 10 days after the last dose of decitabine in each cycle, a DLI product from the previous donor (either remaining from the original transplant unit, or a new unit) will be infused. Donor lymphocytes will be obtained by lymphapheresis from the same allogeneic donor used for transplantation. For local related donors, lymphocyte collections will be performed using standard automated mononuclear cell collection techniques by the University of Minnesota Blood Bank or study affiliate site's institutional guidelines. For unrelated donors or non-local related donors, the lymphocyte collection will be performed at an outside facility according to procedures set by the National Marrow Donor Program. If the collection is non-local, coordination for the timing of the cell collection and the ability to transport the cells to the study site is required. Similarly, for local related donors, the timing of collection (same day as infusion vs. cryopreserved) is according to the collaborating centers' institutional guidelines.

The duration of DLI will be determined according to the collaborating centers' institutional guidelines. DLI will be administered according to a donor-dependent dose-escalation algorithm ([Table 4](#)). In the absence of new GVHD (any grade), the dose of DLI for the next cycle will be higher than the previous cycle. Otherwise, the dose will remain the same. DLI will be given without adding immunosuppressive medications and without conditioning. Addition of immunosuppressive medications as indicated to treat grade I acute GVHD or other non-GVHD steroid-responsive conditions is allowed.

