#### 4 Study Design

This is a multi-center, single-arm, open-label, phase II trial for the frontline treatment of relapsed AML or MDS following allo-HCT.

Eligible subjects will receive up to 4 cycles of combined modality treatment. The number of cycles depends on response, toxicity, and the remaining cell dose.

Cycles include:

- 10 days of decitabine 20 mg/m^2 IV daily; or, alternatively, per institution, physician, or patient preference on a 5-2-5 schedule with no weekend infusion. If a CR is achieved after 2 cycles using the 10-day schedule, subsequent cycles will change to a 5-day schedule.
- Starting with decitabine and continuing for up to 6 months after the end of the last cycle, patients will receive ruxolitinib 5 mg twice daily orally.
- DLI from the original donor will be infused within 10 days after the last dose of decitabine in each cycle.

Patients will be screened for ongoing eligibility before each subsequent cycle of therapy. Patients with disease progression, new GVHD (except grade I acute GVHD), prolongation of the most recent cycle to more than 8 weeks (for any reason), or inadequate cell dose for further DLI will not receive further treatment on study. The DLI dose in each cycle will be

determined according to a donor-dependent dose-escalation algorithm (schema). If the collected cell dose in the DLI is less than the target dose, the patient will receive those collected cells and subsequently removed from further treatment cycles. These subjects will continue to be followed per protocol.

The expected duration of treatment for each subject is 4 cycles of treatment, each lasting 4-8 weeks.

Approximately 34 subjects will be enrolled (32 evaluable) over a period of 24 months, with an additional 12 months of follow up.

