**Table 4: DLI dose escalation algorithm**

	MSD	MUD	Haploidentical
DLI #1, $\times 10^8$ CD3/kg	0.1-1	0.05-0.5	0.01-0.1
DLI #2, $\times 10^8$ CD3/kg	0.5-5	0.1-1	0.05-0.5
DLI #3, $\times 10^8$ CD3/kg	1-10	0.5-5	0.1-1
DLI #4, $\times 10^8$ CD3/kg	5-50	1-10	0.5-5

DLI: Donor lymphocyte infusion; MSD: Matched sibling donor; MUD: Matched unrelated donor

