#### **Inclusion Criteria (on or before Day 1 of Cycles 2-4)**

Patients must meet the following criteria within 7 days prior to day 1 of cycles 2-4 unless otherwise noted.

- 8.5.1** Stable disease or better on bone marrow biopsy within 7 days before cycle 3 (required) and cycles 2 and 4 (if performed). A bone marrow biopsy before cycles 2 and 4 is not required.
- 8.5.2** Additional cells available from the same donor used for the first DLI or the donor willing to donate ([Table 4](#)). This dose will allow for at least one more DLI. Both G-CSF mobilized and unmobilized products are allowed. If a sufficient number of cells for the next DLI is not available, patients will not receive further treatment on study.
- 8.5.3** Adequate organ function:
  - Total bilirubin < 1.5 x upper limit of institutional normal, unless a diagnosis of Gilbert's disease
  - AST/ALT < 2.5 x upper limit of institutional normal
  - Creatinine clearance  $\geq$  40 mL/minute within 3 days prior to day 1, as calculated by the Cockcroft-Gault formula. Cockcroft-Gault CrCl =  $(140 - \text{age}) * (\text{Wt in kg}) * (0.85 \text{ if female}) / (72 * \text{Cr})$ .
- 8.5.4** Peripheral white blood cell count  $< 50 \times 10^9 / \text{L}$  within 3 days prior to day 1. The use of hydroxyurea is allowed and may continue until day 1 of cycle 2.

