#### **Exclusion Criteria (on or before Day 1 of Cycles 2-4)**

Patients must meet the following criteria at the time of screening for the next cycle unless otherwise noted.

- 8.5.5** Active uncontrolled infection. An active uncontrolled infection is defined as hemodynamic instability attributable to sepsis or new symptoms, worsening physical signs or radiographic findings attributable to infection. Persisting fever without signs or symptoms will not be interpreted as an active uncontrolled infection. Subjects with a controlled infection receiving definitive therapy for 72 hours prior to screening are eligible.
- 8.5.6** Any new GVHD except grade I acute GVHD during the most recent cycle.
- 8.5.7** Any form of iatrogenic immunosuppression except  $< 0.5 \text{ mg/kg/day}$  of prednisone or equivalent.
- 8.5.8** Unresolved veno-occlusive disease of the liver, defined as persistent bilirubin abnormalities not attributable to GVHD and ongoing organ dysfunction (renal, ascites).
- 8.5.9** Subjects who are pregnant, breast feeding or sexually active and unwilling to use effective birth control for the remaining duration of the study.
- 8.5.10** Radiation therapy during the most recent cycle.

- 8.5.11** Disease progression during the most recent cycle.
- 8.5.12** Exposure to any other investigational agent, device or procedure during the most recent cycle.
- 8.5.13** Patients or donors with any medical or psychological condition that, in the opinion of the Investigator, might interfere with the subject's continuation in the trial, pose any additional risk for the patient/donor, or confounds the assessments of the subject.
- 8.5.14** Any condition resulting in prolongation of the most recent cycle beyond 8 weeks. If in the view of the investigator, postponing the next cycle is justified for any reason, this is allowed as long as the current cycle does not exceed 8 weeks. If longer than 8 weeks, patients will not receive further therapy on study.
- 8.5.15** Consent withdrawal by patient

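### The hold rule in section 8.2 cannot always be met within Table 4, the row after a hold is not stated, and the target dose that decides removal is only a ten-fold range

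*Combined protocol and SAP*

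**What the plan says.** Section 8.2 sends the reader to Table 4 for the dose of each DLI and then adds a rule that looks back one cycle: "In the absence of new GVHD (any grade), the dose of DLI for the next cycle will be higher than the previous cycle". The other branch is short: "Otherwise, the dose will remain the same".

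Table 4, repeated in the Schema, labels its rows DLI #1 to DLI #4. In units of 10^8 CD3/kg, for sibling, unrelated and haploidentical donors in that order, row #1 reads "0.1-1 0.05-0.5 0.01-0.1" and row #2 reads "0.5-5 0.1-1 0.05-0.5". Row #3 is 1-10, 0.5-5 and 0.1-1. Row #4 is 5-50, 1-10 and 0.5-5.

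Item 8.5.6 decides who can reach the hold branch, because it bars from the next cycle "Any new GVHD except grade I acute GVHD during the most recent cycle". Only new grade I acute GVHD is compatible with going on.

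Two other rules depend on having enough cells. Section 4: "If the collected cell dose in the DLI is less than the target dose, the patient will receive those collected cells", after which the patient is taken off further cycles. Item 8.5.2, which points to Table 4: "If a sufficient number of cells for the next DLI is not available, patients will not receive further treatment on study". Section 6 gives the total needed for four infusions as 66, 16.6 and 1.66 for the three donor types.

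**The concern.** One rule fixes the dose by infusion number and the other by the previous dose. They can disagree after a hold, when the infusion number advances and the dose does not. The removal rule compares a collection with a single target, but the table offers only ranges.

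DLI dose and number of cycles are part of the treatment under test, and the trial runs at several centers. If sites resolve these gaps differently, similar patients receive different doses and different numbers of cycles, and the regimen behind the 6-month survival result is less well defined. There is also a safety side. Section 9.3 describes acute GVHD after DLI as frequent, with reported deaths, and grade III-IV acute GVHD is the only event in the section 15.4 toxicity stopping rule. The unclear step comes just after a patient has shown early GVHD.

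**Working it through.** Doses are in 10^8 CD3/kg. All inputs are the Table 4 entries and the section 6 totals.

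**1. Section 6 totals, the plan's own figures.** Sum of the four upper ends:
- Sibling: 1 + 5 + 10 + 50 = 66; stated 66. Reproduced.
- Unrelated: 0.5 + 1 + 5 + 10 = 16.5; stated 16.6. Off by 0.1.
- Haploidentical: 0.1 + 0.5 + 1 + 5 = 6.6; stated 1.66. Not reproduced; 6.6 / 1.66 = 3.98, about four-fold.

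The lower ends sum to 6.6, 1.65 and 0.66, which fit none of the stated totals. The first three haploidentical upper ends give 1.6, not 1.66.

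**2. Can the held dose sit in the next row?** Read dose as CD3/kg. A hold fits the next row only if the earlier dose is at or above that row's lower end. The part of each row that fails, with its share of the row on the log scale, log(next lower end / own lower end) / log(10):

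| Step | Sibling | Unrelated | Haploidentical |
|---|---|---|---|
| #1 to #2 | 0.1 to <0.5 (70%) | 0.05 to <0.1 (30%) | 0.01 to <0.05 (70%) |
| #2 to #3 | 0.5 to <1 (30%) | 0.1 to <0.5 (70%) | 0.05 to <0.1 (30%) |
| #3 to #4 | 1 to <5 (70%) | 0.5 to <1 (30%) | 0.1 to <0.5 (70%) |

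Example: log(0.5 / 0.1) / log(10) = 0.70. These are shares of the dose range, not of patients. A sibling recipient given 0.1 at DLI #1 must stay at 0.1, but row #2 begins at 0.5.

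**3. Does reading dose as the table row help?** Holding then means staying in row #1 at the second infusion, so the DLI #2 label no longer applies. Because the row is ten-fold wide, the amount infused could still go from 0.1 to 1 in a sibling recipient. The plan does not choose between the two readings.

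**4. The step after a hold.** Suppose DLI #2 is held at the DLI #1 dose and DLI #3 follows its own label. Smallest ratio = row #3 lower end / row #1 upper end; largest = row #3 upper end / row #1 lower end.
- Sibling: 1 / 1 = 1 to 10 / 0.1 = 100.
- Unrelated: 0.5 / 0.5 = 1 to 5 / 0.05 = 100.
- Haploidentical: 0.1 / 0.1 = 1 to 1 / 0.01 = 100.

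From the lower end of row #1 the step is 10- to 100-fold for all three (sibling: 1 / 0.1 = 10 and 10 / 0.1 = 100).

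**5. Target and sufficient.** All twelve cells span exactly ten-fold. A sibling collection of 0.3 for DLI #1 exceeds the lower end (0.1) and is short of the upper end (1). With the lower end as target the patient continues; with the upper end as target section 4 infuses the cells and removes the patient from later cycles. The same split is open in every cell. By step 1, section 6 points to the upper end exactly for siblings, nearly for unrelated donors, and not for haploidentical donors.

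**The case against.** The strongest reply is that Table 4 and the escalation rule stand in the same paragraph and are meant to be applied together. Much of that stands. Each upper end exceeds the one before it, so a higher dose inside the next row always exists, and overlapping rows are not in themselves a conflict. A reader might infer that a compliant site could lower the dose, for example from 1 to 0.5 in a sibling recipient without GVHD. The documents do not support that for a site following both rules with dose read as CD3/kg. A fall needs the row reading, the table taken alone, or a short collection.

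A reader might also infer that a held dose below the next row's minimum triggers removal under section 4. That is strained: section 4 concerns a shortfall in the cells collected, and a hold required by section 8.2 is not a shortfall. Nor do the documents direct sites to skip a level after a hold; they are silent on the row.

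It is also fair that the hold branch is narrow and that the statistical design is untouched. The section 15.3 calculation does not use DLI dose, patients taken off further cycles are still followed (sections 4 and 8.8), and grade III-IV acute GVHD is monitored continuously.

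None of this removes the clash between the hold and the row minimum, the missing rule on which row follows, or the undefined target.

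**Conclusion.** The point holds in two parts.

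First, for patients who continue after new grade I acute GVHD, the hold and the DLI-number rows cannot both be met when the earlier CD3/kg dose lies below the next row's minimum. This can arise at all nine steps. The row that follows a hold is not stated; if the third infusion takes row #3, the step from a held row #1 dose is 1- to 100-fold. The 10- to 100-fold figure is the case that starts from the lower end. The documents give no frequency for grade I acute GVHD, so the number of patients affected cannot be estimated from them.

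Second, the target dose and the sufficient number of cells have no value, so one collection can lead to opposite decisions. This can affect any patient. Section 6 cannot be used to infer that the upper end is the target for every donor type, because its haploidentical total is about a quarter of the upper-end sum.

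The conclusion rests on Table 4 and section 6 as printed. It concerns treatment delivered and patient safety, not sample size or power.

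**What to change.** The sponsor should reconcile section 4, section 6, section 8.2, Table 4 with its copy in the Schema, and item 8.5.2, so that these agree:
- what dose means in section 8.2 (CD3/kg or table row);
- the hold rule and the row labels, including which row applies after a hold;
- what counts as the target in section 4 and as sufficient in 8.5.2;
- the section 6 totals and the Table 4 entries they are meant to reflect.

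The clinical team decides the content; no dose or clinical rule is proposed here. The cost is a protocol amendment to those places. The design, sample size and analysis need no change. Sites may lose some of the freedom that the present ranges give them.

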**Table 4: DLI dose escalation algorithm**

	MSD	MUD	Haploidentical
DLI #1, $\times 10^8$ CD3/kg	0.1-1	0.05-0.5	0.01-0.1
DLI #2, $\times 10^8$ CD3/kg	0.5-5	0.1-1	0.05-0.5
DLI #3, $\times 10^8$ CD3/kg	1-10	0.5-5	0.1-1
DLI #4, $\times 10^8$ CD3/kg	5-50	1-10	0.5-5

DLI: Donor lymphocyte infusion; MSD: Matched sibling donor; MUD: Matched unrelated donor

### 8.3 Monitoring

During infusions, patients will be monitored for occurrence of untoward effects of the infusion of allogeneic lymphocytes such as rash, acute allergic reaction, bronchospasm, respiratory distress, acute vascular leak syndrome, localized or systemic infections.

### 8.4 Ruxolitinib Dose modification

Dose adjustment for ruxolitinib is recommended ([Table 5](#)).

**Table 5: Ruxolitinib dose adjustment**

CTCAE grade 3 or greater bleeding related to low platelets	Non-transfused platelets		
	<10 $\times 10^9$ /L	10-50 $\times 10^9$ /L	>50 $\times 10^9$ /L
Hold. Reassess 2 weeks after resolution of bleeding	Hold	5 mg daily	5 mg twice daily 

For cycles 2, 3, and 4, if platelets improve to  $>100 \times 10^9$ /L, a dose increase to 10 mg twice daily may be considered.

### 8.5 Re-screening Eligibility for Cycles 2- 4

Patients will be screened for eligibility to continue onto each subsequent cycle of therapy. Patients with disease progression, new GVHD (except grade I acute GVHD), prolongation of the most recent cycle to more than 8 weeks (for any reason), or inadequate cell dose for further DLI will not receive further treatment on study. Rescreening will be an ongoing process. When patients meet the eligibility criteria outlined below, they may begin subsequent cycles.

#### **Inclusion Criteria (on or before Day 1 of Cycles 2-4)**

Patients must meet the following criteria within 7 days prior to day 1 of cycles 2-4 unless otherwise noted.

- 8.5.1** Stable disease or better on bone marrow biopsy within 7 days before cycle 3 (required) and cycles 2 and 4 (if performed). A bone marrow biopsy before cycles 2 and 4 is not required.
- 8.5.2** Additional cells available from the same donor used for the first DLI or the donor willing to donate ([Table 4](#)). This dose will allow for at least one more DLI. Both G-CSF mobilized and unmobilized products are allowed. If a sufficient number of cells for the next DLI is not available, patients will not receive further treatment on study.
- 8.5.3** Adequate organ function:
  - Total bilirubin < 1.5 x upper limit of institutional normal, unless a diagnosis of Gilbert's disease
  - AST/ALT < 2.5 x upper limit of institutional normal
  - Creatinine clearance  $\geq$  40 mL/minute within 3 days prior to day 1, as calculated by the Cockcroft-Gault formula. Cockcroft-Gault CrCl =  $(140 - \text{age}) * (\text{Wt in kg}) * (0.85 \text{ if female}) / (72 * \text{Cr})$ .
- 8.5.4** Peripheral white blood cell count  $< 50 \times 10^9 / \text{L}$  within 3 days prior to day 1. The use of hydroxyurea is allowed and may continue until day 1 of cycle 2.

#### **Exclusion Criteria (on or before Day 1 of Cycles 2-4)**

Patients must meet the following criteria at the time of screening for the next cycle unless otherwise noted.

- 8.5.5** Active uncontrolled infection. An active uncontrolled infection is defined as hemodynamic instability attributable to sepsis or new symptoms, worsening physical signs or radiographic findings attributable to infection. Persisting fever without signs or symptoms will not be interpreted as an active uncontrolled infection. Subjects with a controlled infection receiving definitive therapy for 72 hours prior to screening are eligible.
- 8.5.6** Any new GVHD except grade I acute GVHD during the most recent cycle.
- 8.5.7** Any form of iatrogenic immunosuppression except  $< 0.5 \text{ mg/kg/day}$  of prednisone or equivalent.
- 8.5.8** Unresolved veno-occlusive disease of the liver, defined as persistent bilirubin abnormalities not attributable to GVHD and ongoing organ dysfunction (renal, ascites).
- 8.5.9** Subjects who are pregnant, breast feeding or sexually active and unwilling to use effective birth control for the remaining duration of the study.
- 8.5.10** Radiation therapy during the most recent cycle.

- 8.5.11** Disease progression during the most recent cycle.
- 8.5.12** Exposure to any other investigational agent, device or procedure during the most recent cycle.
- 8.5.13** Patients or donors with any medical or psychological condition that, in the opinion of the Investigator, might interfere with the subject's continuation in the trial, pose any additional risk for the patient/donor, or confounds the assessments of the subject.
- 8.5.14** Any condition resulting in prolongation of the most recent cycle beyond 8 weeks. If in the view of the investigator, postponing the next cycle is justified for any reason, this is allowed as long as the current cycle does not exceed 8 weeks. If longer than 8 weeks, patients will not receive further therapy on study.
- 8.5.15** Consent withdrawal by patient

## **8.6 Supportive Care**

Supportive care will be provided per institutional guidelines and standard of care. The investigator may prescribe any concomitant medications or treatment deemed necessary to provide adequate supportive care. Supportive care may include antibiotics, anti-fungals, analgesics, transfusions, growth factors.

Patients with recent CNS involvement should continue on CNS therapy (chemotherapy or radiation) as medically indicated during the protocol.

## **8.7 General Concomitant Medication Guidelines**

- Coadministration with potent CYP3A inhibitors; consider alternative agents with less CYP3A inhibition
- Coadministration with potent CYP3A4 inducers.
- If concomitant administration of an anticoagulant/antiplatelet medication is indicated, then caution and enhanced monitoring is required. History of thrombocytopenia should be a factor in the choice of anticoagulant and dose.

## **8.8 Duration of Study Treatment**

The expected duration of treatment for each subject is 4 cycles of treatment, each cycle lasting 4 weeks; with up to 4 weeks of rescreening for eligibility to continue on to subsequent cycles; followed by six additional months of ruxolitinib. The following may be reasons for removal from additional study treatment:

- unacceptable toxicity
- disease progression

- new GVHD (except grade I acute GVHD)
- prolongation of the most recent cycle to more than 8 weeks (for any reason)
- inadequate cell dose for further DLI
- consent is withdrawn or patient is not compliant

Patients who are unable to receive further DLIs after initial cycle(s), may continue to receive ruxolitinib as long as the physician believes they are benefiting from the treatment, the patient has not withdrawn consent, and they have not developed unacceptable toxicity.

All patients receiving at least one cycle of treatment will be followed per [Sections 11.1](#) and [11.2](#) and be evaluable per [Section 15](#).

Patients unable to continue DLI may be treated per physician's choice. These patients will still be followed per [Sections 11.1](#) and [11.2](#).

